7.4. Subgroup Analysis

When the following demographic and baseline characteristics are available, the subgroup analyses will be performed for safety and efficacy endpoints as specified in this plan.

1. Male vs. Female,
2. Treatment emergent Anti-Drug Antibodies (ADA) status (ADA positive vs. ADA negative):

Treatment emergent ADA positive are patients with either:

- (1) Titer boosted: patients who were IgG positive to pegunigalsidase alfa at baseline and boosted post treatment (i.e., titer increase by at least 4-fold from baseline. See Shankar et al. 2014), or
 - (2) Treatment induced: patients who were IgG negative to pegunigalsidase alfa at baseline and positive at any timepoint post treatment.
3. Baseline Fabry disease (FD) classification (classic / non-classic):

For this analysis, FD Classic is defined as $\leq 5\%$ mean of lab normal ranges

residual enzymatic activity in plasma or leukocytes (baseline) and at least one Fabry specific symptoms (baseline): Cornea Verticillata, Acroparesthesias, and/or Angiokeratomas.

In addition, the eGFR slopes analysis will also be analyzed according to other subgroups specified in Section 10.1.3.

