8. EFFICACY AND SAFETY ASSESSMENTS

8.1 Safety Variable(s)

- Safety will be assessed by the frequency, severity, and duration of treatment-emergent AEs (see Section 8.3, Adverse Events), including clinically significant laboratory abnormalities, ECG changes from baseline, physical examination findings and assessment of the injection site after administration of the study drug
- Anti-Drug (i.e., PRX-102) IgG antibodies will be assessed before dosing with PRX-102 at baseline (Visit 1). Anti-PRX IgG antibodies will be assessed every month for the first 6 months and every 3 months until the end of study through the last infusion. If a patient continues treatment in an extension study, the anti-drug antibodies will be assessed as part of that study. For patients who end treatment with PRX-102, anti-PRX-102 antibodies will be assessed 1 and 3 months after last infusion
- Anti-Drug IgE antibodies will be assessed in events of hypersensitivity reaction following Sponsor request
- Ability to taper off infusion premedication at the start of the study
- Requirement for use of premedication overall to manage infusion reactions

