9.1.3. Treatment-Emergent Adverse Events (TEAE)

Number and percent of patients with at least one TEAE as well as the number of TEAE in the following categories will be summarized overall and by the subgroups presented in Section 7.4:

- Any TEAE
- Treatment non-related (unlikely, not-related) TEAE
- Treatment related (defined as possibly, probably or definitely related) TEAE
- Mild or moderate TEAE
- Treatment related mild or moderate TEAE
- Severe TEAE

- Treatment related severe TEAE
- Serious TEAEs
- Treatment related serious TEAE
- TEAE leading to withdrawal
- Treatment related TEAE leading to withdrawal
- TEAE leading to death
- Treatment related TEAE related to death.

These tables above will be repeated for the number and percentage of patients with at least one injection site reaction TEAE.

Summary tables will be presented for the frequency of any TEAEs by the MedDRA SOC and PT by overall and by the subgroups presented in Section 7.4; by the MedDRA SOC and PT and severity of TEAE; by MedDRA SOC and PT, and the relationship of TEAEs to study drug.

Summary tables will be presented for the frequency of serious TEAEs by the MedDRA SOC and PT for overall and by gender and by the MedDRA SOC and PT and relationship to study drug.

In the summaries of severity and relationship to study drug, the most extreme outcome (highest severity and closest relationship to study drug) will be used for those subjects who experience the same TEAE (per preferred term) on more than one occasion.

Missing values associated with TEAEs will be treated as missing except for causality, intensity, and outcome of a TEAE, at which occurrence a “worst case” approach will be taken in the analysis. Thus

- If causality is missing, the TEAE will be regarded as related to pegunigalsidase alfa
- If the intensity is missing, the intensity of the AE will be regarded as severe
- If the outcome is missing and the stop date is not provided, the outcome is regarded as “ongoing”.
- If the seriousness is missing, all efforts should be made prior to database lock to make sure that this information is available, if still missing, the worst-case scenario is assumed.

If there were any TEAEs leading to withdrawal or death, these cases will be presented by patient.

Listing of TEAE will include also the TEAE onset and end date and also relative to first pegunigalsidase alfa infusion.

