9.1.5. Infusion Related Reactions (IRR)

The IRRs are those treatment emergent adverse events (TEAE) which occurred during the infusion or within 2 hours after the completion of the infusion and the causality of the adverse events are determined to be definitely, probably, or possibly related, based on the the site reports in the eCRF.

Injection site reactions which are not considered IRR are excluded from the summary of IRRs, and will be identified based on their SOC and PT, as listed in the following table:

MedDRA SOC	MedDRA Preferred Term
General disorders and administration site conditions	Infusion site discomfort
	Injection site discomfort
	Infusion site pain
	Injection site pain
	Infusion site hematoma
	Injection site hematoma
Injury poisoning and procedural complications	Contusion
	Procedural site reaction
	Procedural pain
Vascular disorders	Vein rupture

The number and percentage of IRRs in the following categories will be summarized for overall, and by gender, FD Classification, and Treatment Emergent pegunigalsidase alfa ADA. The percentage will be based on the total number of IRRs of the population or subset. In addition, the number and percentage of IRR will be summarized by administration location (Home/Site). The summary will include the

following categories:

- Overall number of IRR (used to calculate the percentage),
- Mild or Moderate IRR,
- Severe IRRs,
- Very Severe IRRs,
- Serious IRR.
- IRR that lead to study discontinuation
- IRR that lead to death

Number and percentage of patients with IRRs by MedDRA SOC and PT will be summarized for overall, and by gender, FD Classification, and Treatment Emergent ADA. The number and percentage of patients with IRRs by MedDRA SOC and PT and severity will be summarized for overall.

Number of IRRs by MedDRA SOC and PT will be summarized for overall, and by gender, FD Classification, and Treatment Emergent pegunigalsidase alfa ADA. The number of IRRs by MedDRA SOC and PT and severity will be summarized as well for overall.

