9.6. Treatment-emergent Anti-Pegunigalsidase alfa Antibodies

Treatment emergent anti-pegunigalsidase alfa antibodies (ADA+ vs. ADA-) is defined in Section 7.4.

The number and percentage of patients who are Treatment emergent ADA will be summarized by visit

An overall anti-pegunigalsidase alfa antibodies status per patient during the study (“positive” if positive at any visit, negative if negative at all visits), will be summarized as well.

Analyses will be repeated by gender and by Fabry disease classification (classic/non-classic).

Note to programmer: The treatment-emergent anti-pegunigalsidase alfa antibodies (ADA) including the three test results:

- a. IgG = negative if ‘IgG Screening (Presumptive Pos/Neg)’ (LBTEST) for LBSCAT = for PRX-102 is Negative; otherwise the status will be determined based on the result of ‘IgG Immunodepletion (Pos/Neg)’ : Positive or Negative,
- b. Neutralizing Antibody = the result of ‘Neutralizing Antibody (Pos/Neg)’ (LBTEST): Positive or Negative,
- c. IgE = the result of ‘IgE Screening (Presumptive Pos/Neg)’ (LBTEST): Positive or Negative.

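### TEAEs and infusion reactions are split by a post-baseline, ever/never ADA status that SAP 7.4 lists as a baseline characteristic, with no link to when the first positive sample was taken

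*SAP*

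**What the plan says.** SAP 7.4 introduces its subgroup factors with "When the following demographic and baseline characteristics are available" and lists treatment-emergent ADA status beside sex and Fabry classification. A patient is ADA positive in one of two ways. Treatment-induced patients are "patients who were IgG negative to pegunigalsidase alfa at baseline and positive at any timepoint post treatment". Titer-boosted patients were already IgG positive at baseline and showed a "titer increase by at least 4-fold from baseline". Neither route attaches a date to the status.

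The status is then used to split safety events:

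- SAP 9.1.3 tabulates TEAEs "by overall and by the subgroups presented in Section 7.4".
- SAP 9.1.5 states "Number of IRRs by MedDRA SOC and PT will be summarized for overall, and by gender, FD Classification, and Treatment Emergent pegunigalsidase alfa ADA", and splits patients with IRRs in the same way.
- An IRR is timed to the infusion only: it is a related event "which occurred during the infusion or within 2 hours after the completion of the infusion".
- Percentages in the IRR category summary use the number of IRRs in the population or subset as denominator.

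SAP 9.6 tabulates ADA by visit and gives an overall ever-positive status. Its programmer note begins "The treatment-emergent anti-pegunigalsidase alfa antibodies (ADA) including the three test results" and lists IgG, neutralizing antibody and IgE. IgE is taken as the screening result, with no comparison to baseline. Protocol 8.1 says "Anti-Drug IgE antibodies will be assessed in events of hypersensitivity reaction following Sponsor request". The flow charts in both documents schedule IgG only.

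**The concern.** A status that depends on any later sample is not known at baseline. When it is used to group events over the whole year, a reaction at the first infusion in a patient who first tests positive at Visit 14 is counted as an ADA-positive reaction. The ADA-positive column therefore mixes events before and after the antibody was detected.

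Safety is the primary objective, and both IRRs and treatment-emergent antibodies are named safety endpoints (SAP 3.2.1). Protocol 6.2 notes that immunogenicity and hypersensitivity may differ between the two products. Premedication is tapered in the first two months and infusion time may later be shortened, so reaction risk may change over the year for reasons unrelated to antibodies. An ever/never split cannot separate these influences. With IRR counts as denominator, it also cannot show a reaction rate per infusion before and after seroconversion.

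The comparison group is mixed too. A patient who is IgG positive at Visit 1 and never has a 4-fold rise meets neither positive definition, and so falls with the ADA negatives. This matters in patients switching from agalsidase alfa, because Protocol section 4 reports cross-reactivity of antibodies to the enzyme.

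**Working it through.** The plan gives no figure for this point, so there is none to reproduce. The check is a count from the schedule.

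**Inputs**

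- Infusions: every two weeks at Visits 1 to 27, so 27 for a patient who completes (Protocol 6.1 and section 9).
- Scheduled IgG samples: Visit 1, then Visits 3, 5, 7, 9, 11, 14, 20 and 27 (flow charts).
- Samples are taken before that visit's infusion (Protocol 9.1.3 and 9.1.5 to 9.1.9).

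**Infusions before the first positive sample.** If the first positive is at Visit v, then v − 1 infusions precede it, a share of (v − 1)/27. This is the most that can have preceded antibody onset. If the previous scheduled sample, at Visit u, was negative, and a negative result is taken to mean no antibody, then at least u − 1 infusions preceded onset.

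| First positive at | Upper bound (v − 1) | Previous sample | Lower bound (u − 1) | Infusions in between |
|---|---|---|---|---|
| Visit 3 | 2 (7.4%) | Visit 1 | 0 | 2 |
| Visit 5 | 4 (14.8%) | Visit 3 | 2 (7.4%) | 2 |
| Visit 9 | 8 (29.6%) | Visit 7 | 6 (22.2%) | 2 |
| Visit 14 | 13 (48.1%) | Visit 11 | 10 (37.0%) | 3 |
| Visit 20 | 19 (70.4%) | Visit 14 | 13 (48.1%) | 6 |
| Visit 27 | 26 (96.3%) | Visit 20 | 19 (70.4%) | 7 |

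**From infusions to IRRs.** These are shares of infusions. The share of an ADA-positive group's IRRs that precede first positivity is the sum over v of w(v) × H(v − 1). Here w(v) is the fraction of the group first positive at Visit v, and H(k) is the fraction of IRRs falling in the first k infusions. The documents give neither, so both are assumed:

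- Flat IRR rate, first positives spread evenly over Visits 3, 5 and 7: (2 + 4 + 6)/(3 × 27) = 12/81 = 14.8%.
- Flat rate, first positives spread evenly over all eight samples: (2 + 4 + 6 + 8 + 10 + 13 + 19 + 26)/(8 × 27) = 88/216 = 40.7%.
- IRR rate 4 times higher in infusions 1 to 5: 35.7% and 58.3% for the same two onset patterns.
- IRR rate 10 times higher in infusions 1 to 5: 51.4% and 71.5%.

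A range of about 15% to 72% from plausible-looking inputs shows only that the share cannot be stated from the documents.

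**Whether timing enters elsewhere.** SAP 9.6 gives ADA frequency by visit. The TEAE listing in SAP 9.1.3 gives onset relative to the first infusion. Listings 7.3, 9.2 and 9.4 cover IgG, TEAEs and infusion-related events. No planned table joins an event date to an antibody result.

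**The case against.** The strongest reply is that ever/never treatment-emergent status is a legitimate description of patients, and that status at the time of an event answers a different question. That stands, and is why the ever/never tables should be kept. It does not justify calling the status a baseline characteristic, or leaving the event-level question without a table.

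Second, with 22 planned patients a reader could work out the order of events from the listings. This is partly right, but SAP 11.3 allows those listings to be replaced by raw-data listings, and a hand search gives no denominator.

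Third, the TEAE and IRR tables by ADA are counts and percentages, with no test or measure of association planned. This also stands. No error rate or decision rule depends on them.

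Some stronger readings are tempting but unsupported:

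- A reader might infer that reactions will be shown to have happened before antibodies appeared. The first positive sample is not onset, and six or seven infusions separate the samples at Visits 14, 20 and 27.
- A reader might take the infusion shares as shares of misassigned IRRs. That needs an IRR time pattern, and assuming one largely assumes the answer.
- A reader might infer that IgE distorts the ADA groups. SAP 7.4 uses IgG only, so the IgE issue is one of labelling in SAP 9.6.
- A reader might infer from Protocol 8.1 that no antibody sample is drawn at a reaction unless the Sponsor asks. Protocol Appendix 3 calls for antibody blood samples at the onset of any listed sign without that condition, though it names no isotype.

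**Conclusion.** The point holds as a limited but real weakness. If the SAP is followed exactly, reactions before the first positive sample are counted as ADA positive, and nothing in the planned tables shows how many. For first positives at Visits 5, 9 and 14, at most 15%, 30% and 48% of the 27 infusions precede antibody onset. The corresponding floors are 7%, 22% and 37%, if a negative sample is taken as absence of antibody. These figures assume all 27 infusions are given and only scheduled samples are used. The share of IRRs affected is unknown.

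The consequence is for the reading of descriptive tables on a named safety endpoint. The documents do not support a claim that an association will be created or hidden, only that the planned tables could not reveal either.

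For IgE, no baseline measurement is scheduled, so the treatment-emergent label is unsupported as planned. Protocol 9.1.3 lists a Visit 1 antidrug antibody sample without isotype. The documents neither plan nor exclude later IgE testing of it, and do not say that serum is stored.

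**What to change.** 1. In SAP 7.4, label ADA status as post-baseline. Keep the ever/never tables as a clearly labelled descriptive display.
2. Add TEAE and IRR tables that classify each event by treatment-emergent status at the last sample before onset. Status begins at the first positive result for patients negative at Visit 1, and at the first titer rise of at least 4-fold for patients positive at Visit 1. Use infusions given in each state as denominator.
3. Show events between the last negative and first positive sample as a separate category (for Visit 1 positives, between the last sample below the 4-fold rule and the first that meets it).
4. Use reaction-triggered antibody samples (Protocol Appendix 3), where they yield an IgG result, to help date the first positive.
5. Add Visit 1 anti-pegunigalsidase IgG status, already derived in SAP 8.3, as a subgroup for these tables. SAP 8.3 refers to the screening result and SAP 9.6 adds immunodepletion, so one rule should serve both.
6. In SAP 9.6, report IgE as event-triggered, and call it treatment-emergent only where a Visit 1 sample is available and tested negative.

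The IgG part uses data already planned for collection and costs SAP wording and programming. The cells will be small and sparse, and status between the widely spaced samples at Visits 14, 20 and 27 will remain uncertain. Any IgE assay on Visit 1 serum depends on a usable sample remaining.

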7.5. Interim Analysis

An interim analysis was performed when approximately 80% of the patients completed or discontinued the study to support the Biologics License Application (BLA). The analyses were conducted based on SAP dated 24 June 2019. Additional clarification to the SAP and new analyses were described in Notes to Files (NTF). Additional analyses conducted at the interim analysis were not pre-specified. The CSR dated 6 March 2020 is based on the interim analysis provided details on the changes from the SAP and the analyses that were not pre-defined.

For the final analyses, the Sponsor plans to repeat the analyses performed in the CSR and conduct some new analyses. This SAP described all of these planned analyses. The new analyses will not have an impact on study interpretation.

8. DEMOGRAPHICS AND STUDY SUMMARY

8.1. Subject Disposition

The number and percentage of subjects who were screened, enrolled, treated, completed, and discontinued will be summarized. The documented reasons for screen failures will be tabulated. The number and percentage of subjects who discontinued will also be summarized for each reason of discontinuation, and their last completed scheduled visits. The number of subjects in each of the analysis population (Safety, efficacy and Per-Protocol) will be presented.

8.2. Demographics

The demographics (age, gender, race, and ethnicity) will be summarized using descriptive statistics by gender and overall. The analysis will be repeated for the Safety and Efficacy sets.

8.3. Baseline Characteristics

The baseline characteristics will be summarized by descriptive statistics overall and by each of the subgroups described in section 7.4. The analysis will be repeated for the Safety and Efficacy sets.

Continuous variables:

- Age started Fabry therapy
- % residual enzyme activity in leukocyte (defined as the value in leukocyte \times 100/83.5, where 83.5 is the mean of reference range)
- % residual enzyme activity in plasma (defined as the value in plasma \times 100/12.95, where 12.95 is the mean of reference range)
- eGFR
- pre-switch eGFR annualized slope
- Plasma Lyso-Gb3
- Plasma Gb3
- Urine Lyso Gb3

Categorical variables:

- Fabry disease (FD) classification (classic / non-classic) (See Section 7.4)
- UPCR classified into four categories (See Section 10.4)
- Presence of Proteinuria (UPCR \geq 0.5 gr/gr / $<$ 0.5 gr/gr)
- Treatment with ACEi or ARBs (yes/no). Status is yes if there is any concomitant medication of ACE or ARB taken before baseline visit, otherwise it will be determined based on the answer to the question ‘patient is NOT treated with an ACE inhibitor or ARB’.
- Premedication use (yes / no: premedication used for agalsidase alfa infusions before enrolment)
- anti Replagal Immunogenicity status (ADA-positive or ADA- negative to agalsidase alfa (REPLAGAL). The determination of the status is based on the results of the IgG Screening for REPLAGAL.
- anti pegunigalsidase alfa Immunogenicity status (ADA-positive or ADA- negative to pegunigalsidase alfa. The determination of the status is based on the results of the IgG Screening for PRX-102.

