4.1. Sample Size and Statistical Power Consideration

No formal sample size calculation has been performed for this study.

The sample size of 22 patients is adequate to evaluate the safety of switching from agalsidase alfa to pegunigalsidase alfa in this orphan disease in which patient recruitment in clinical trials is difficult.

4.2. Study Flow Chart:

Activity	Screening Period		Visits Treatment Period Pegunigalsidase alfa						
	Screening Visit (-3 Month)	Visit A (-2 Month) and B (-1 Month)	Visit 1	Visits 2, 4, 6, 8, 10, 12, 13, 15, 17, 19, 21, 23, 25, 26	Visits 3, 5, 9, 11	Visits 7, 20 (Months 3 and 9)	Visit 14 (Month 6)	Visits 16, 18, 22, 24	Visit 27 (Month 12)
Sign IC	x								
Assign screening number	x								
Medical history	x								
Demographics	x								
Alpha-galactosidase activity in plasma and leucocytes	x								
Historical serum creatinine	x								
Vital signs (blood pressure, pulse, temperature and respiration)	x		x	x	x	x	x	x	x
Body weight	x		x			x	x		x
Body height	x								
Physical examination	x		x			x	x		x
Concomitant medications (including pain and premedications)	x	x	x	x	x	x	x	x	x
Hematology	x		x			x	x		x
Biochemistry	x		x			x	x		x
Serum Creatinine and Cystatin C	x	x	x		x	x	x	x	x
Urinalysis – dipstick	x		x			x	x		x
Protein/Creatinine ratio spot urine test	x	x	x			x	x		x
HbsAg, HCV & HIV	x								
Serum pregnancy test (beta HCG)	x		x						
Urine Lyso Gb3 concentration	x		x			x	x		x
Plasma Lyso Gb3	x		x			x	x		x
Plasma Gb3	x		x			x	x		x

Activity	Screening Period		Visits Treatment Period Pegunigalsidase alfa						
	Screening Visit (-3 Month)	Visit A (-2 Month) and B (-1 Month)	Visit 1	Visits 2, 4, 6, 8, 10, 12, 13, 15, 17, 19, 21, 23, 25, 26	Visits 3, 5, 9, 11	Visits 7, 20 (Months 3 and 9)	Visit 14 (Month 6)	Visits 16, 18, 22, 24	Visit 27 (Month 12)
Anti-pegunigalsidase alfa Antibodies (IgG)			x		x	x	x		x
Electrocardiography (ECG)	x		x			x	x		x
Chest X-ray	x								
Cardiac function assessment (echocardiography and stress test)	x		x				x		x
Cardiac MRI			x				x		x
Inclusion/exclusion criteria	x								
Request for subject approval	x								
Enrollment approval		x ¹							
Mutation analysis			X						
PrT, PTT	X								
C3, C4	x								
Vit D	x								
Short Form Brief Pain Inventory (BPI)			x			x	x		x
Brain MRI			x						x
Mainz Severity Score Index (MSSI)			x				x		x
EQ-ED-5L			x				x		x
Pegunigalsidase alfa infusion + clinical observation			x	x	x	x	x	x	x
Adverse event assessments		x	x	x	x	x	x	x	x

1 After Visit B

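### SAP 8.3 sets baseline anti-pegunigalsidase alfa status from the screening assay alone, while SAP 9.6 lets immunodepletion settle any non-negative screen, so the baseline tables can over-call antibody positivity

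*SAP*

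**What the plan says.** Three SAP sections bear on whether a patient counts as antibody-positive at baseline.

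- **Section 8.3 (Baseline Characteristics)** lists anti-pegunigalsidase alfa status as a categorical baseline variable and gives its rule: "The determination of the status is based on the results of the IgG Screening for PRX-102". It names no confirmatory step. It also asks for baseline characteristics overall and by each Section 7.4 subgroup, one of which is treatment-emergent antibody status.
- **Section 9.6 (Treatment-emergent Anti-Pegunigalsidase alfa Antibodies)** has a programmer's note introduced by "The treatment-emergent anti-pegunigalsidase alfa antibodies (ADA) including the three test results". For IgG, a negative screen is negative; "otherwise the status will be determined based on the result of" the IgG immunodepletion test. The variable name quoted there marks the screening result as presumptive. For the definition of treatment-emergent status the section points elsewhere: "Treatment emergent anti-pegunigalsidase alfa antibodies (ADA+ vs. ADA-) is defined in Section 7.4".
- **Section 7.4 (Subgroup Analysis)** gives two routes to treatment-emergent positivity. Treatment-induced patients are "patients who were IgG negative to pegunigalsidase alfa at baseline and positive at any timepoint post treatment". Titer-boosted patients are IgG positive at baseline with at least a 4-fold rise in titer. Neither route names the assay tier that decides baseline IgG status, and neither refers to 8.3.

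The sample in question is the pre-dose Visit 1 sample (Protocol 8.1).

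**The concern.** One blood sample falls under two classification rules. A patient whose Visit 1 sample screens positive and fails immunodepletion is antibody-positive by 8.3 and IgG-negative by 9.6. The SAP does not say which prevails for the baseline row.

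Baseline status matters in this trial. Every patient has had at least two years of agalsidase alfa. The protocol's introduction describes cross-reactive alpha-GAL-A antibodies between the existing enzymes, and Protocol 6.2 says immunogenicity may differ between the two products. Safety is the primary objective, and treatment-emergent antibody is a listed safety endpoint. A reader will use the baseline antibody row to separate antibody already present from antibody that appeared after the switch.

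The conflict is most visible in Tables 14.1.4.2.1 and 14.1.4.2.2, which present baseline characteristics by treatment-emergent antibody status. Suppose 7.4 is programmed with the 9.6 rule. An unconfirmed baseline positive who then seroconverts is classed as treatment-induced, which requires a negative baseline. The same table prints that patient as antibody-positive at baseline, and a reader would take the case for a boosted one.

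**Working it through.** The plan states no assay false-positive rate, baseline antibody prevalence or antibody-based sample size, so it has no figure of its own to reproduce. The check is a comparison of rules, followed by an illustration of scale.

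**1. The two rules on one Visit 1 sample**

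| Screening | Immunodepletion | 8.3 baseline status | 9.6 IgG status |
|---|---|---|---|
| Negative | not used by the rule | Negative | Negative |
| Positive | Positive | Positive | Positive |
| Positive | Negative | **Positive** | **Negative** |

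The rules differ only in the third row, and only in one direction. The count of screening positives can equal or exceed the count of confirmed positives but cannot fall below it.

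**2. Scale in the baseline tables**

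Inputs:
- N = 22, the planned size (SAP 4.1).
- f = screening false-positive rate. Assumed: 1%, 5%, 10%.
- q = share of patients truly negative at baseline. Assumed: 1 and 0.5.

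Formulas: expected unconfirmed positives = 22 × q × f; chance of at least one = 1 − (1 − f)^(22q).

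| f | Expected, q = 1 | P(at least one), q = 1 | Expected, q = 0.5 | P(at least one), q = 0.5 |
|---|---|---|---|---|
| 1% | 0.22 | 1 − 0.99^22 = 20% | 0.11 | 1 − 0.99^11 = 10% |
| 5% | 1.1 | 1 − 0.95^22 = 68% | 0.55 | 1 − 0.95^11 = 43% |
| 10% | 2.2 | 1 − 0.90^22 = 90% | 1.1 | 1 − 0.90^11 = 69% |

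One patient moves the baseline antibody-positive percentage by 1/22 = 4.5 points.

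**3. Does the difference reach treatment-emergent status?**

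- If 7.4 takes baseline IgG from the 9.6 rule, an unconfirmed positive is baseline-negative and can still qualify as treatment-induced. Seroconversions missed: 0.
- If a programmer instead carries the 8.3 flag into 7.4, that patient can qualify only through the 4-fold titer route. Let s be the seroconversion rate. As an assumed range I take 25% to 88%, which the protocol's introduction reports for male patients in early studies of the existing enzymes. With f = 5% and q = 1, the expected number at risk of being missed is 22 × 0.05 × 0.25 = 0.28 to 22 × 0.05 × 0.88 = 0.97, before removing any patient still counted as boosted.

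**4. Effect of the fix**

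With the 9.6 rule used in 8.3, the third row of the first table becomes negative in both columns, and the disagreement is zero by construction.

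**The case against.** The strongest reply is that this is one descriptive row. The note in 9.6 is written for the treatment-emergent variable and is not limited to post-baseline samples, so its natural reading covers Visit 1 as well. Section 9.6 refers to 7.4 for the definition, and 7.4 does not cite 8.3. On that reading the adverse event, infusion reaction, eGFR slope, biomarker, pain and clinical-event subgroups are all derived correctly. **This stands.**

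A reader might go further and infer that seroconversions will be missed and treatment-emergent antibody biased downward. The documents do not support that. It needs a link from 8.3 to 7.4 that is nowhere stated. A reader might also infer that an unconfirmed positive would have no baseline titer against which to measure a 4-fold rise, but no section says which samples are titered. Nor can one say that Table 14.3.4.6 will contradict the baseline tables. Only its title is given, and the shells are in a separate document.

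The scale figures also depend on assumptions. Taking all 22 as truly negative is the least favorable case for the plan. After two or more years on a related enzyme some true baseline positives are plausible, and they cannot be false positives. That is why the half-negative column is shown.

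What the reply does not remove is the conflict itself. Section 8.3 states a rule for baseline status that 9.6 does not accept as final for the same test. Section 8.3 is also the only place that expressly defines a baseline anti-pegunigalsidase alfa status, so its use as the input to 7.4 cannot be ruled out while 7.4 names no assay tier.

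**Conclusion.** The point holds for the baseline tables. As written, 8.3 can report unconfirmed screening positives as antibody-positive in Tables 14.1.4.x and can disagree with the 9.6 status of the same Visit 1 sample. Any error is toward over-calling.

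Its size is unknown. The illustrative chance of at least one affected patient runs from 10% (f = 1%, half truly negative) to 90% (f = 10%, all truly negative). Both f and q are assumptions, since the documents give neither.

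Bias in treatment-emergent antibody is a conditional risk, not a finding. It arises only if the 8.3 flag is used in 7.4; under the natural reading of 9.6 it is nil. This is a small inconsistency, worth correcting because the baseline row is read alongside a safety endpoint.

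**What to change.** - **In 8.3**, define baseline anti-pegunigalsidase alfa status by the 9.6 rule: negative if the screen is negative, otherwise the immunodepletion result.
- **In 7.4**, state that IgG positive and IgG negative at baseline mean this confirmed status.
- **For anti-Replagal status**, which 8.3 also bases on screening, label the row as screening-only unless a confirmatory result exists. Section 9.6 gives a confirmatory rule for pegunigalsidase alfa only, so the same correction cannot be assumed to be available.

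The cost is a few lines of SAP text and a change to one derived variable. Section 9.6 already names the immunodepletion result, so no new data collection is needed.
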